4.2.1.2. Identification of duplicate cases

The Diabetes Database was designed to prevent the entry of more than one record for any patient due to the uniqueness of the medical record number. Occasionally, however, a patient is mistakenly assigned more than one medical record number, thereby permitting a duplicate entry in the Diabetes Database. Each month a query is run to identify patients in the SEARCH database who have matching entries for medical record number or date of birth and last name. This method allows two opportunities to identify duplicate records. When duplicate records are identified, these records are reviewed to confirm that they are duplicates. True duplicate records are marked as duplicates in the SEARCH database.

For expanded sources of case identification, duplicates are identified by comparing our Diabetes Database to the lists provided by our network partners as described above. DOB duplication is investigated further to eliminate duplicate cases entered due to spelling errors or name changes or interchange of first and middle names. Duplicates are eliminated before cases are added to the SEARCH database.

4.2.1.3. Case definition and eligibility

Prevalent cases were defined as either: a) physician diagnosis of diabetes or b) parent or self-report of physician diagnosis. Prevalent cases include all cases less than 20 years of age who lived in the 8-county primary service area for CCHMC at anytime during the index year of 2001. College students were counted according to their reported residence location during 2001. Military personnel and institutionalized cases were excluded.

4.2.2. Incident Cases

4.2.2.1. Case finding site-specific approaches

Primary Source for Case Identification

The primary source for identification of incident cases is the Diabetes Database maintained by the Division of Endocrinology at CCHMC. In 1988 a database of diabetes patients seen at CCHMC since 1978 was established by review of their medical records. This database continues to be updated on a regular basis.

The investigators review the patient's medical record to confirm validity and to insure that the subject meets the eligibility criteria for an incident case.

Patients who live in the 8-county primary service area are identified via their zip codes. All patients who meet the eligibility criteria for incident cases are contacted to verify that they live in the 8-county geographic area. Patients who are attending college and live outside the geographic area are excluded.

Expanded Sources for Case Identification

Expanded case identification was done to identify subjects who meet the eligibility criteria, yet who have never been seen at CCHMC. The same network partners established to identify prevalent cases were used to assist us in identifying 2002 and 2003 incident cases: 1) endocrinologists, 2) diabetes educators, 3) insurance companies, 4) hospitals, 5) city and state health departments, and 6) primary care physicians who care young people with diabetes who meet the eligibility criteria without endocrinology referral. Due to low yield from expanded providers, efforts for 2004 were limited to the

most productive: 1) adult endocrinologists, 2) hospitals, 3) hospital based CDE's, and 4) The Cincinnati Health Department.

We return periodically to these network partners to request a list of newly identified cases. In order to protect patient confidentiality, these lists include the minimum amount of PHI required to de-duplicate cases and collect core data. We have obtained a waiver from the IRB at CCHMC to expedite data collection from providers outside of the hospital. We compare the information provided to our Diabetes Database to identify new cases, as well as duplicates. If a medical record is available on a new case, it is reviewed either by a representative of the outside provider or by a SEARCH Study team member to validate and determine eligibility of the case. In situations where a record is not available such as an insurance provider, the physician of record is asked to validate the case. Most of our network partners have agreed to mail information about this study including an IPS to all newly identified cases. Before returning the completed survey, subjects are asked to check a box on the cover of the survey indicating whether or not they wish to be contacted with additional information on the study. They are contacted only if they indicate a desire to receive more information. New cases will be assigned a unique identification number. A limited amount of data to include; date of birth, date of diagnosis, type of diabetes, race, gender, county and zip code will be added to the SEARCH database under the ID number. Name will be assigned as either Jane or John Doe depending on the gender. If the survey is returned, the subjects name and all contact information will be added to the database.

Case definition and eligibility

Incident cases are defined as either: a) physician diagnosis of diabetes or b) parent or self-report of physician diagnosis. Incident cases include all cases less than 20 years of age on 12/31 of the onset years of 2002, 2003, 2004 and who lived in the 8-county primary service area for CCHMC at the time of diagnosis. College students were counted according to their reported residence location at the time of onset. Institutionalized cases and military personnel were excluded.

4.3. CASE VALIDATION

4.3.1. Completeness of case ascertainment

4.3.1.1. Prevalent cases

All visits to the diabetes inpatient unit and the diabetes outpatient treatment center were entered into a clinical diabetes database. Each month using a unique medical record number these diabetes visits were compared to the SEARCH Database to

identify new cases. New cases with a diabetes diagnosis or with the diagnosis omitted are then downloaded from this clinical database to the SEARCH Database. All cases not previously included in the database are marked for further review. Medical records are then reviewed to confirm that the patient indeed has diabetes, to classify the type of diabetes, and to determine eligibility. Confirmed, eligible cases are then registered.

To capture young people seen by other CCHMC departments, an administrative report was requested regularly from the CCHMC billing database. This report included all inpatients and outpatients born after 12/31/1981 who were seen at CCHMC with either a primary or secondary 250.xx ICD-9 code and lived in one of the eligible counties as determined by zip code.

We used our network partners (endocrinologists, diabetes educators, insurance companies, hospitals, and city and state health departments) to maximize the sensitivity of our expanded case-finding outside CCHMC.

The source(s) of each validated case was recorded, i.e. Diabetes Database within CCHMC, endocrinologist, insurance company, school nurse, etc. This information was then be used to determine the capture-recapture estimates for completeness of ascertainment.

In addition, by comparing observed to expected ratios by age group and county and by confirming an increase in prevalence with age, face validity and consistency within the site was evaluated. Rate consistency among sites was reviewed and an explanation of any inconsistencies was pursued to justify disparities.

4.3.1.2. Incident cases

All visits to the diabetes inpatient unit and the diabetes outpatient treatment center are entered into a clinical diabetes database. Using a unique medical record number, these diabetes visits are compared monthly to the SEARCH Database to identify new cases. New cases with a diabetes diagnosis or with the diagnosis omitted are then downloaded from this clinical database to the SEARCH Database. All cases not previously included in the database are marked for further review. Medical records are then reviewed to confirm that the patient indeed has diabetes, to classify the type of diabetes, and to determine eligibility. Valid, eligible cases are then registered.

Additional cases seen at CCHMC but not by the Endocrinology Service are captured by a regularly requested CCHMC administrative report. This report is compared to the SEARCH database and a chart review is performed for all “new” cases to confirm validity and eligibility prior to registration.

Due to the low yield from many of the expanded sources pursued for prevalent, incident 2002, and incident 2003 case finding, we will use only the Diabetes database at CCHMC, the administrative report from CCHMC, Adult Endocrinologists, hospitals, hospital based CDE's, and the Cincinnati Health Department for future incident case finding.

The source(s) of each validated case will be recorded, i.e. Diabetes Database within CCHMC, endocrinologist, insurance company, school nurse, etc. This information will then be used to determine the capture-recapture estimates for completeness of ascertainment.

We will review observed to expected ratios by age group and county as a tool to evaluate face validity and consistency within the site. Consistency among sites will be evaluated and an explanation of any inconsistencies will be pursued to justify disparities.

4. Methodology of Case Ascertainment – South Carolina

SEARCH – South Carolina seeks to document the incidence and prevalence of diabetes among South Carolina children and adolescents. Incident cases will be identified by recording all youth newly diagnosed with diabetes in South Carolina aged 0-19 beginning 1/01/2002. To identify prevalent cases, SEARCH South Carolina will record all youth aged 0-19 with a diagnosis of diabetes in 2001 in the four South Carolina counties of Richland, Lexington, Orangeburg, and Calhoun.

GOAL

To ascertain and validate all unique (non-duplicated) cases of diabetes in youth aged 0-19 years in defined geographic areas in defined periods of time. This will allow estimation of prevalence and incidence rates by age, gender, and ethnicity.

4.1. DENOMINATOR ESTIMATION

4.1.1. Site specific approaches

The 2000 US Census non-institutionalized non-military (NI-NM) resident population from which cases are present in the index year will be used as the primary denominator in sites using geographic-based denominators such as South Carolina. Use of this denominator will most closely align the population at risk for all sites.

Special Populations

College students: Such individuals are counted in the Census in their residence location as of April 1 2000, usually the college/town where they attend school. They will be included in the NI-NM denominators. There are three large research universities (University of South Carolina, Clemson University, and the Medical University of Charleston) and nine teaching colleges and universities within the South Carolina geographic area of interest. South Carolina also has 22 independent and private colleges and universities. Contact with the school(s) health services will be made to determine the estimated number of known cases, and the school's willingness to participate.

Military personnel: Military personnel are counted in the Census for the county in which they currently reside/are based. Initial total population estimates include them, however, as the Census results are further refined, the military members are identified separately. Final denominator estimates will exclude military service members, though they will be included in less refined estimates. There are three large military bases in South Carolina: Fort Jackson Army Base, Shaw Air Force Base, and the US Marine Corps Recruiting Depot - Parris Island. Fort Jackson, located in Richland County, is the largest basic training facility for the army, graduating approximately 40,000 soldiers each year. Shaw Air Force Base,

located in Sumter County, supports approximately 6,500 military and civilian workers and 6,000 family members.

Native American Reservation residents: There are various Native American tribes residing in South Carolina. These include two federally recognized tribes: the Catawba and the Cherokee. The Catawba reservation lies within the South Carolina borders. Other non-federally recognized tribes include: the Lumbee (primarily North Carolina), the Pee Dee, the Chicora, the ChicoraWaccammaw, the Edisto, and the Santee. Census data will be used for identifying the number of Native Americans in general. From previous work with the Catawba, we expect to be able to determine tribal-specific rates for the Catawba Nation by using the Catawba tribal roles for denominator data. Whether the other nations keep accurate tribal roles for tribal specific rates is unclear.

Persons living in group settings: The group quarters population includes all people not living in households. Two general categories of people in group quarters are recognized:

- a) The institutionalized population that includes people under formally authorized, supervised care or custody in institutions at the time of enumeration (such as correctional institutions, nursing homes, and juvenile institutions). These will be identified separately and removed from the denominator.
- b) Non-institutionalized population that includes all people who live in group quarters other than institutions (such as military quarters, and group homes.) These will be removed resulting in the non-institutionalized, non-military population used as the primary denominator for all geographic sites.

Denominator estimation by age, gender, ethnicity

Age categories (0-4, 5-9, 10-14, 15-19) from the 2000 census will be used to calculate rates. Gender (M, F) and ethnic categories from the 2000 census will also be used, and ethnic groups will be collapsed into more inclusive groups (e.g. Non-Hispanic White, Hispanic American, African American, Asian, Pacific Islander, Native American) using rules developed by the census.

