4.2. DENOMINATOR ESTIMATION

Overview

To estimate incidence and prevalence accurately, it is necessary to align the numerator and the denominator. That is, the cases of diabetes that are counted in the numerator for prevalence and incidence must derive from the same population that is defined as the denominator. To estimate incidence and prevalence accurately, it is also necessary to have accurate information on the denominator of children 0-19 years of age in which diabetes cases exist (for prevalence) or occur (for incidence). Every effort will be made in SEARCH to assure that numerator and denominator are aligned by applying the same criteria for inclusion in the denominator to eligibility for the study and to include case-finding data sources that would identify cases that would arise from the denominator.

The four geographically based SEARCH centers (Cincinnati, Colorado, Seattle, South Carolina) will use the US Census non-institutionalized non-military resident population in the area from which cases are drawn as the total denominator for estimation of prevalence and incidence. For the prevalence component of the study, 2000 US Census data will be used. For the incidence component of SEARCH, the geographically based centers will use projections of population changes based on the 2000 Census. A resident is defined by the Census as a person with a permanent address within the defined

geographic area at any time in the index year, who is not noted to be living elsewhere or only temporarily residing at the eligible address.

The membership-based centers (Hawaii and Southern California) will use administrative data on membership 0-19 years in the participating health plans as the total denominator for estimation of both incidence and prevalence. For both the prevalence and incidence components of the study, the number of health plan members on July 1 in the given year will be used.

Special populations

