4.2.1. Prevalence Component**4.2.1.1. Eligibility Criteria**

The eligibility criteria for prevalent cases of diabetes are as follows:

- a. Prevalent in 2001,

- b. Age less than 20 years on December 31, 2001; this corresponds to a birth year: 1/1/82 – 12/31/2001 for the prevalence year of 2001. Subjects reaching age 20 in the prevalence year are not eligible,
- c. Resident of the population defined for prevalent cases at any time in the prevalence year (for geographically-based centers) or member of the participating health plan in the prevalence year,
- d. Not active-duty military,
- e. Not living in an institution (defined as such by the Census),
- f. Not gestational diabetes.

For geographically-based centers, resident is defined to align numerator and denominator and includes anyone documented to have resided in that center's geographical area at any time during the prevalence year.

Prevalent cases of diabetes in active duty military personnel are ineligible because it is anticipated that access to military medical records will be difficult. It is unlikely that the prevalent diabetes cases will be present among active duty military because diabetes precludes active duty military service.

Prevalent cases of diabetes in dependents of military personnel having access to civilian medical facilities will be eligible, recognizing that prevalent diabetes cases receiving care only at military facilities can be ascertained only if access to military records is obtained.

Prevalent cases of diabetes in college students are eligible for SEARCH as these youth are counted in the Census as resident at their college address. Additionally, college students identified as cases by membership-based centers cannot be removed from the membership-based administrative records that are the source of denominator data for these centers.

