4.2.1.2. Case definition and eligibility

Prevalent cases will be identified via a) a physician diagnosis of diabetes or b) parent or self-report of physician diagnosis.

A “physician diagnosis” of diabetes is considered to have been identified if any of the following methods are used: a) record review for physician diagnosis of diabetes; b) direct verification of case status by knowledgeable physician (or other health care provider directly involved in care); or c) location in clinically verified database (where case has been verified by a clinician). In South Carolina, all initial contact with patients or their parents will be made through a physician, who has previously verified case status.

The following eligibility criteria will apply to all prevalent cases:

- a. Index year: 2001
- b. Birth year: 1/1/1982 – 12/31/2001
- c. Age range: 0 – 19.999 in 2001
- d. Geographic area: Richland, Lexington, Orangeburg, and Calhoun Counties in South Carolina.
- e. Non-institutionalized, non-military resident/member of population from which cases are present in the index year

Military personnel: Such individuals are not part of the Census denominators for non-institutionalized, non-military (NI-NM) personnel. Fort Jackson Army base is the only major military installation in Richland, Lexington, Orangeburg, and Calhoun counties. Active duty personnel automatically receive medical care through Moncrief Army Community Hospital’s (MACH) Family Health Center (FHC). Dependents of active military members who live on base or within a 30 minute driving radius also qualify for treatment through FHC. Those dependents who live outside the 30-minute radius plus all retirees and their dependents are referred to a Primary Care Manager (PCM) and receive their medical care from the surrounding community. We will not seek cases from Moncrief Army Community Hospital. Military members or military dependents will be identified at initial contact.

College students: College students are eligible, as they will be included in the non-institutionalized, non-military denominator. Contact with the school(s) health services will be made to determine the number of known cases, and to develop methods for further contact.

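### South Carolina's group-quarters rule contradicts the protocol's own denominator and, if applied literally, would bias that center's rates upward

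*Protocol*

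**What the plan says.** **The removal rule.** South Carolina section 4.1.1 states that "The group quarters population includes all people not living in households". It splits them into (a) the institutionalized, who are removed, and (b) the non-institutionalized, described as "all people who live in group quarters other than institutions (such as military quarters, and group homes.) These will be removed". The section presents this second step as "resulting in the non-institutionalized, non-military population used as the primary denominator for all geographic sites".

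**The study-wide denominator.** Under Section 4.2 the four geographic centers "will use the US Census non-institutionalized non-military resident population". The special-populations text there takes out active-duty military and people in institutions, and keeps college students in both numerator and denominator. It does not exclude group quarters as such.

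**College students in South Carolina.** On the denominator, section 4.1.1 says "They will be included in the NI-NM denominators". On the numerator, section 4.2.1.2 says "College students are eligible, as they will be included in the non-institutionalized, non-military denominator", and the incident-case section (4.2.2.1) repeats this.

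**Other eligibility.** South Carolina's prevalent cases must be a "Non-institutionalized, non-military resident/member of population from which cases are present in the index year". The study-wide criteria (4.2.1.1 and 4.2.2.1) exclude active-duty military and people living in an institution. Neither set excludes residents of group homes or other civilian group quarters.

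**The concern.** Item (b) names one population and describes a subtraction that produces another. Its own class is the non-institutionalized part of group quarters, so removing all of it deletes civilian youth who belong to the target population.

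Two groups are affected:

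- **Group homes** are named as removed, yet their residents remain eligible as cases.
- **College housing** is not named. But (a) and (b) are the only classes offered, and students who live neither in a household nor in an institution fall into (b).

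Section 4.2 requires numerator and denominator to come from the same population. Item (b) breaks that by shrinking the denominator alone, which pushes rates up, mainly at the oldest ages if college residents are the larger group.

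The step is still to come. South Carolina section 4.1.2 says a state office will make the non-institutional, non-military subsets, after which prevalence is updated. Item (b) is the most detailed instruction for that work, and an analyst following it would get a different denominator from one following the college-student paragraph.

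**Working it through.** **1. Do the planning figures already contain the subtraction?**

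- Incidence: South Carolina in Table V-10 is 539,046 + 578,976 = 1,118,022, which is the Table 3-2 figure. Appendix 2 of the South Carolina section (full Census count) less its Other column is 1,135,778 − 17,747 = 1,118,031. The difference of 9 comes from one cell, non-Hispanic white aged 0-9: 319,654 in the appendix and 319,645 in Table V-10.
- Prevalence: South Carolina in Table V-9 is 85,707 + 95,817 = 181,524. Appendix 1 less Other is 184,757 − 3,233 = 181,524. Table 3-1 gives 179,238, which is 1.3% lower and unexplained.
- Precision: the age-specific denominators in Table 6-1 (1,758,692 and 1,759,650) are the column sums of Table V-9. The total in Table 6-2 (5,072,988) is that of Table V-10.

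The counts behind the projections and precision tables are therefore full Census counts less Other. No group-quarters subtraction is visible.

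**2. Size if item (b) is applied literally.**

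Inputs from Appendices 1 and 2:

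- Four counties: 23,262 aged 18-19; 27,826 + 23,262 = 51,088 aged 15-19; 184,757 aged 0-19.
- Statewide: 126,137 aged 18-19; 169,240 + 126,137 = 295,377 aged 15-19; 1,135,778 aged 0-19.

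Let g be the share of 18-19 year-olds in civilian, non-institutional group quarters. The protocol gives no value, so 5-50% is an assumption. Suppose nobody younger is removed and every case is still counted. For a band of N youth, of whom n are aged 18-19:

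inflation = N / (N − g·n) − 1, which at ages 18-19 is 1/(1 − g) − 1.

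Example, four counties, 15-19, g = 20%: 0.2 × 23,262 = 4,652; 51,088 / 46,436 − 1 = 10.0%.

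| g (assumed) | 18-19 | 15-19, four counties | 15-19, statewide | 0-19, four counties | 0-19, statewide |
|---|---|---|---|---|---|
| 5% | +5.3% | +2.3% | +2.2% | +0.6% | +0.6% |
| 20% | +25% | +10.0% | +9.3% | +2.6% | +2.3% |
| 50% | +100% | +29% | +27% | +6.7% | +5.9% |

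South Carolina's own rate bands are five-year, so 15-19 is the band to read. The 18-19 column matters because Section 8.1.1 also plans single-year estimates.

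**3. Offset from missed college cases.** If a fraction u of cases among these residents is never found, and their rate equals that of other 18-19 year-olds, the rate ratio at 18-19 is (1 − g·u)/(1 − g). At g = 20% it is 1.25 with u = 0, 0.90/0.80 = 1.125 with u = 0.5, and 1.00 with u = 1.

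**4. Scale.** South Carolina expects 361 prevalent cases, so the sampling half-width for its overall prevalence is about 1.96/√361 = 10.3%. The 0-19 bias stays below that throughout the assumed range, but more years of data would not reduce it.

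**The case against.** The strongest reply is that item (b) is loose drafting and not a decision. The college-student paragraph in the same subsection, and both South Carolina eligibility sections, expressly keep students in. Item (b) never mentions colleges, and it names as its product the same population that Section 4.2 defines, which suggests that the military was the intended target. Removing service members housed in military quarters is correct, and in Richland County, home of Fort Jackson, they may be a large part of group quarters.

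Much of this stands. A reader might infer that South Carolina has settled on dropping students from the denominator while counting their cases. The documents do not support that: they contradict each other on students, and those living in households stay in under either reading. Nor do they support a fixed inflation at ages 18-19. The share is undocumented, any figure that includes military residents would overstate it, the Appendix counts are unrefined Census totals, and college case-finding still depends on whether schools agree to take part. Group homes alone give no reason for an effect specific to 18-19.

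Two other inferences should be resisted. The four-county total of 169,880 in South Carolina section 4.1.2.1 is 8.1% below the 184,757 in Appendix 1, but nothing ties that gap to group quarters. And although item (b) claims to describe all geographic sites, no other geographic center's section describes such a removal.

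The reply does not rescue the sentence. Group homes need no inference: they are removed from the denominator and left in the numerator. The instruction also cannot produce the population it names.

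**Conclusion.** Item (b) is wrong as written. It conflicts with Section 4.2, with South Carolina's own college-student text and with the case eligibility criteria. For group homes it is a direct mismatch of unknown size; for college residents it is an internal contradiction that takes effect only if item (b) is followed when the final subsets are made.

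In that event South Carolina rates are biased upward, by about 2% to 29% at ages 15-19 and 0.6% to 7% at ages 0-19 (5% to 100% at ages 18-19 alone). These ranges rest on an assumed civilian group-quarters share of 5-50% at ages 18-19, no removals at younger ages and complete case capture; under-capture of college cases would shrink or cancel the bias. Projected case counts and the precision tables do not carry the problem.

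**What to change.** Reword item (b) so that only military personnel are removed from the non-institutional group-quarters population, and state that civilian residents, including those in college housing and group homes, stay in the denominator. The wording should refer to personnel and not to military quarters, because Section 4.2 and South Carolina's military paragraph exclude service members as persons wherever they live. Make the phrase about all geographic sites match Section 4.2, or delete it. Give the same definition to the state office that prepares the population subsets.

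The cost is one sentence and a different Census subtraction. No planning table needs recalculating. If any South Carolina denominators have already been prepared under item (b), they should be rebuilt before rates at ages 15-19 are reported or pooled.
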